4.3.4 Rationale for GM-CSF Induction Dose and Schedule

GM-CSF may enhance antigen presentation, in which case a priming dose of GM-CSF prior to checkpoint inhibitor administration could be sufficient to enhance T cell activation.

Alternatively, GM-CSF may increase the numbers of Fc receptor bearing antigen-presenting cells to enhance the activation of T cells by providing a cellular scaffold for a checkpoint inhibitor. With this mechanism, GM-CSF may need to be administered simultaneously with a checkpoint inhibitor in order to potentiate T cells.

We hypothesize that any potential contribution of GM-CSF will be most important during a priming or “induction” phase of treatment. This study will examine the efficacy of a novel induction regimen of GM-CSF administered at a fixed dose of 250 μ g SC once daily on days 1-14 every 21 days for 2 cycles (6 weeks), in combination with pembrolizumab at fixed dose of 200 mg IV every 21 days as above, based upon the observed efficacy of this GM-CSF dose and schedule in combination with ipilimumab in metastatic melanoma, and in similar combinations in prostate cancer and pancreatic cancer.³³⁻³⁵

For the initial Safety Cohort (Stage 1) of 9 patients, pembrolizumab was initiated as a single agent on Cycle 1, Day 1, and GM-CSF was administered days 1-14 in Cycles 2 and 3. A planned interim safety analysis showed that the incidence of \geq Grade 3 adverse events adjudicated as at least possibly treatment-related to the combination of GM-CSF plus pembrolizumab met criteria to continue with study enrollment (see Section 8.5.1). Enrollment to Efficacy Cohort (Stage 2) was subsequently completed with 18 additional patients. In the Efficacy Cohort, GM-CSF was initiated concurrently with pembrolizumab starting Cycle 1, Day 1 for two induction cycles, based upon the rationale that priming by GM-CSF is optimized if administered in advance or concurrently with PD-1 inhibition.

Acknowledging that the optimal duration and schedule of GM-CSF induction is unknown, re-induction with GM-CSF for 2 additional cycles is allowed in patients who demonstrate CR, PR, or prolonged SD with evidence of clinical benefit after the Induction Phase and within 12 months from enrollment, but who subsequently progress on single-agent pembrolizumab between

approximately 6-12 months (corresponding to Cycle 8-16) after enrollment (after the primary endpoint of PFS6 has been ascertained for that patient) (see Section 7.1.5.1). Repeat GM-CSF induction requires approval on a case-by-case basis from the Study Chair. Re-induction (r) PFS (rPFS and rPFS6) and response rate (rRR) will be described in these cases.

If ≥ 5 patients (approx. 20%) undergo GM-CSF re-induction and demonstrate restored CR or PR within 6 months after re-induction, the study team will consider whether to amend the protocol to allow for prolonged GM-CSF treatment or serial re-induction depending on the observed outcomes.

4.3.5.1 Rationale for Expansion Cohort Schedule and Biopsies

An important exploratory objective of the Expansion Cohort is to obtain paired biopsy samples from patients while on treatment with pembrolizumab monotherapy and in combination with GM-CSF, in addition to archival pre-treatment samples. Correlative analyses of tumor and TIIC PD-L1 expression, TIIC profiles, and PBMC profiles will explore for changes associated with

pembrolizumab alone and with addition of GM-CSF to better understand the differential contributions of each study drug to the observed clinical and radiographic responses in this study.

To enable comparisons of pembrolizumab monotherapy and in combination with GM-CSF, the schedule for the Expansion Cohort will be the same as the Safety Cohort, starting with 1 cycle of pembrolizumab monotherapy before adding induction GM-CSF during Cycles 2 and 3. The observed safety and efficacy of the Safety Cohort and Efficacy Cohort are similar, though limited by small sample sizes, supporting the choice of the Safety Cohort schedule for the Expansion Cohort. Biopsies will be planned during Week 3 of pembrolizumab monotherapy and Week 9 after addition of GM-CSF and after first restaging imaging has been obtained. PMBC profiles will be compared between the Safety and Expansion Cohorts (expected n=23) and the Efficacy Cohort (n=18), enabling further characterization of the impact of GM-CSF on immune cell profiles in a larger group of subjects.

4.3.6 Rationale for Endpoints

4.3.6.1 Primary Efficacy Endpoint: Overall Response Rate (ORR)

Based upon results from Stages 1 and 2 indicating a promising proportion of patients with durable radiographic and clinical responses, the primary endpoint for this study will be changed to overall response rate (ORR) by locally-assessed RECIST 1.1,¹ previously a key secondary endpoint, and %PFS6 will be changed to a key secondary endpoint. In advanced biliary cancer patients treated with standard 2nd-line chemotherapies, the historical response rate is approximately 10% with short duration of response,^{2,4} and there is no standard therapy approved by the FDA in this context owing to limited efficacy. In unselected advanced biliary cancer patients treated with pembrolizumab monotherapy in KEYNOTE-158, the response rate has not yet been reported. A target ORR of 20% (H_1) on treatment with pembrolizumab plus induction GM-CSF would represent a meaningful improvement in this population, with H_0 5% as null hypothesis in the absence of any established effective standard 2nd line therapy in advanced biliary cancers.

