1.0 TRIAL SUMMARY

[figure not shown]
Abbreviated Title	Pembrolizumab plus GM-CSF Induction in Advanced Biliary Cancers
Trial Phase	II
Clinical Indication	Advanced biliary cancers including unresectable intrahepatic or extrahepatic cholangiocarcinoma and gall bladder carcinoma
Trial Type	Open label, single arm phase II therapeutic clinical trial
Type of control	None
Route of administration	Intravenous (pembrolizumab) and subcutaneous (GM-CSF)
Trial Blinding	N/A
Treatment Groups	N/A (not randomized)
Number of trial subjects	Total enrollment of 42 subjects for expected PFS6-evaluable n=40 and overall response evaluable n=37, combined between the following three cohorts: Stage 1: n=9 (completed) Stage 2: n=18 (completed) Expansion Cohort: n=15
Estimated enrollment period	Stages 1 and 2: 16 months (completed); Expansion Cohort: 12 months
Estimated duration of trial	52 months for accrual plus up to 2 years on treatment from start of treatment of last enrolled patient in the Expansion Cohort, with potential for up to 2 additional years of survival follow up in event that last patient has prolonged stable disease and discontinues without progression after 24 months or 35 cycles
Duration of Participation	Expect median time on pembrolizumab treatment of 6 months

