8.3 Definition of Study Endpoints

8.3.1 Primary Endpoint

The primary endpoint was amended to be overall response rate (**ORR**) with addition of Expansion Cohort, based upon the promising responses observed during Stages 1 and 2 (Safety and Efficacy Cohorts). **ORR** is defined as the proportion of subjects with RECIST 1.1-measurable disease at study entry who have a complete response (CR) or partial response (PR) (confirmed + unconfirmed) using RECIST 1.1¹ at any time during the main study. Measurable disease has been added as a required inclusion criterion for Expansion Cohort eligibility. Re-induction and Second Course ORR (rORR, sORR) will be determined based upon response after first dose of re-induction or first dose of Second Course. Subjects with measurable disease at study entry who have unknown or missing response information will be treated as non-responders. Subjects with non-measurable disease at study entry will be excluded from ORR and DOR analyses.

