8.4 Sample Size and Accrual Rate

8.4.1 Sample Size

For the primary endpoint of ORR, a sample size of 37 response-evaluable subjects will provide power of 77% with 2-sided 5% alpha and 88% with 1-sided 5% alpha to show ORR improvement from H_0 of 5% to H_1 of 20%, under protocol treatment. Based upon a subset with non-measurable disease enrolled to Stages 1 and 2 before amendment requiring RECIST 1.1-measurable tumors for enrollment to Expansion Cohort, along with potential for dropout in this population with comorbidity of biliary obstruction and liver disease, it is estimated that total enrollment of 42 subjects will include at least 37 response-evaluable subjects.

The key secondary endpoint of %PFS6 was previously the primary endpoint for Stages 1 and 2, prior to amendment adding Expansion Cohort, which also changed to primary endpoint of ORR based upon the promising response rate observed in Stages 1 and 2. For the key secondary endpoint of PFS, an expected overall study PFS-evaluable sample size of at least 40 patients will have power 78% with 2-sided alpha 5% and power 87% with 1-sided alpha to show PFS improvement from H_0 of 20% to H_1 of 40% on protocol therapy.

Pre-amendment, a Simon's 2 stage design was employed to determine if adequate efficacy was observed in Stage 1 to warrant proceeding to Stage 2. The pembrolizumab/GM-CSF combination was considered worthy of additional investigation if the true %PFS6 is 50%, and hence the alternative hypothesis, $\%PFS_1=0.50$. Therefore assuming an α error probability of 5%, and a β error of 20%, the first stage had 9 patients. If ≤ 2 of 9 had been observed progression-free, the study would not proceed to second stage. Since ≥ 3 of 9 patients are observed progression-free at 6 months (4/9 achieved PFS6 in Stage 1), enrollment continued to the second stage with 18 additional patients, with a goal of at least 24 evaluable patients (with planned over-enrollment of 3 additional patients to account for expected 10% dropout rate). If ≤ 9 patients are observed progression-free at 6 months out of 24 evaluable patients by the end of second stage, then no further investigation of the drug is warranted under this PFS6 hypothesis. Conversely, if ≥ 10 patients are progression-free at 6 months among Stages 1 and 2 subjects, the study would be considered positive for the hypothesis: H_0 : $\%PFS_0 < 25\%$ versus H_a : $\%PFS_1 > 50\%$.

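### ORR became primary because Stage 1-2 responses looked promising, and the same patients are pooled into its test; the quoted 77%/88% power and 5% alpha are fixed-sample figures that ignore this

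*Combined protocol and SAP*

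**What the plan says.** The trial opened as a Simon two-stage design with %PFS6 as primary endpoint and ORR as a key secondary one. Section 4.3.6.1 introduces the change with "Based upon results from Stages 1 and 2 indicating a promising proportion of patients with durable radiographic and clinical responses, the primary endpoint"; Sections 8.1, 8.3.1 and 8.4.1 give the same reason.

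The cohorts in Section 1.0 are "Stage 1: n=9 (completed) Stage 2: n=18 (completed) Expansion Cohort: n=15", so 9 + 18 = 27 of the 42 patients belong to the stages that prompted the change. Sections 3.1 and 8.5.2 define the ORR analysis over all cohorts, restricted to evaluable patients with measurable disease. Section 8.4.1 expects that "total enrollment of 42 subjects will include at least 37 response-evaluable subjects", and states that "a sample size of 37 response-evaluable subjects will provide power of 77% with 2-sided 5% alpha and 88% with 1-sided 5% alpha" for a null ORR of 5% against 20%. Section 8.6.1 repeats these figures.

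The text reviewed contains no conditional critical value, no separate ORR for the Expansion Cohort, and no statement that the pooled test is nominal. The original PFS6 decision rule is still in Section 8.4.1.

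**The concern.** An encouraging run of early responses is both the reason for testing ORR and a large part of the evidence in that test. The quoted alpha and power treat all 37 outcomes as unobserved when the hypothesis was fixed. A reader of the final report meets a primary ORR p-value only because the early responses were good, so the false-positive probability that matters to that reader is the one given the switch.

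The trial is uncontrolled and open-label, with locally assessed response that counts confirmed and unconfirmed responses. A nominally significant pooled ORR could therefore rest mainly on the data that generated the hypothesis, with little contribution from the only new patients. The pooled point estimate has the same selection built into it.

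**Working it through.** **Inputs.** From Section 8.4.1: 37 evaluable patients, null ORR 5%, alternative 20%. From Section 1.0: 27 patients in Stages 1-2 and 15 in the Expansion Cohort.

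Assumed: m = 22 to 25 of the 37 evaluable patients come from Stages 1-2, that is 37 − 15 = 22 if every Expansion patient is evaluable and 37 − 12 = 25 if 12 are. Also assumed: the switch is made when Stage 1-2 responders S reach at least k.

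**Reproducing the plan's figures.** With X ~ Bin(37, p):
- 1-sided 5%: cut-off 5. P(X ≥ 5 | 0.05) = 3.6%; P(X ≥ 5 | 0.20) = 88.8% (stated 88%).
- 2-sided 5%, upper tail 2.5%: cut-off 6. P(X ≥ 6 | 0.05) = 0.95%; P(X ≥ 6 | 0.20) = 77.8% (stated 77%).

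The stated figures are therefore correct for a fixed single-stage sample of 37, with no allowance for the endpoint change.

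**Probability of rejection given the switch.** With E responders among the n = 37 − m Expansion patients and cut-off c:

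P(reject | S ≥ k) = Σ_{s≥k} P(S = s) · P(E ≥ c − s) / P(S ≥ k)

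Example with m = 22, k = 3 and true ORR 5%: P(S ≥ 3) = 0.0948. The joint probability of switching and rejecting is 0.0262 at cut-off 5 and 0.0082 at cut-off 6. The ratios are 27.6% and 8.6%.

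| Switch if S ≥ | False positive at 5%, cut-off 5 | False positive at 5%, cut-off 6 | Power at 20%, cut-off 5 | Power at 20%, cut-off 6 |
|---|---|---|---|---|
| 2 | 9.8-11.2% | 2.7-3.1% | 91-92% | 80-81% |
| 3 | 24-28% | 7.1-8.6% | 94-96% | 84-87% |
| 4 | 57-62% | 21-25% | 98-99% | 92-94% |

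Ranges run over m = 22 to 25.

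**Unconditional probability.** The chance of switching and then falsely rejecting ORR, with m = 22 and cut-off 5, is 3.4%, 2.6% and 1.4% for k = 2, 3 and 4. It cannot exceed 3.6% at cut-off 5 or 0.95% at cut-off 6, because it is part of the event that X reaches the cut-off.

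**Given the exact count already seen** (m = 22, n = 15), the test needs E ≥ c − s:

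| Responders seen | True 5%: cut-off 5 / 6 | True 20%: cut-off 5 / 6 |
|---|---|---|
| 2 | 3.6% / 0.5% | 60% / 35% |
| 3 | 17% / 3.6% | 83% / 60% |
| 4 | 54% / 17% | 96% / 83% |
| 5 | 100% / 54% | 100% / 96% |

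With five already seen, 0/15 in the Expansion Cohort would still pass cut-off 5.

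**Bias.** With m = 22, k = 3 and true ORR 5%, E(S | S ≥ 3) = 3.28. The expected pooled ORR is (3.28 + 15 × 0.05)/37 = 4.03/37 = 10.9%, about twice the truth.

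**The case against.** The strongest reply is that the ORR test does not exceed its nominal level unconditionally. That is true: a reader might infer that the 5% level is broken outright, and the binomial bound above rules that out for ORR taken alone. Error above 5% in the unconditional sense arises only from having two routes to a positive trial. With the original PFS6 rule at 4.8% and endpoints assumed independent, 1 − (1 − 0.048)(1 − 0.036) gives about 8.3% with the 1-sided ORR rule, and the same sum with 0.0095 gives about 5.8% with the 2-sided rule.

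The size also depends on figures not seen here. The Stage 1-2 responder count, evaluable count and switching rule are absent from the text reviewed. Section 4.3.3 points to the Expansion Cohort rationale for the response rate, and the text just before Section 4.3.5.1 was unavailable. It would be wrong to state as fact that 22 outcomes were known: Section 8.4.1 expects dropout, and Section 8.3.1 counts a response at any time in the main study.

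A reader might also infer that power is overstated. The documents do not settle that. Averaged over a switch rule, power is above the stated values; for a specific count it can fall either way.

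A further tempting step is to say that the pooled PFS6 test has the same fault because "4/9 achieved PFS6 in Stage 1" was already known. It does not follow. PFS6 was the original primary endpoint and was demoted, not selected, and continuing past Stage 1 was a planned rule. Under that rule (at least 3/9, then at least 10/24, null 25%), the conditional error after 4/9 is P(X ≥ 6 | 15, 0.25) = 14.8%, while the design's overall alpha is 4.8%. High conditional error after a good first stage is normal there. The move of the PFS6 hypotheses from 25%/50% to 20%/40% is a separate matter.

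Finally, the switch is disclosed, ORR was already a key secondary endpoint, and this is a single-arm phase II trial. Disclosure helps, but it does not make the quoted alpha and power describe the design being run.

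**Conclusion.** The point stands in conditional form. The figures quoted as "power of 77% with 2-sided 5% alpha and 88% with 1-sided 5% alpha" are arithmetically right for 37 prospectively tested patients and do not describe a test whose endpoint was chosen after many of those patients' responses had been seen. Given the switch, the false-positive probability at a true ORR of 5% is above the fixed-sample 3.6%/0.95% for every threshold tried. It ranges from modest (about 10-11% / 3% for a switch at two or more) to large (57-62% / 21-25% at four or more). The pooled estimate is biased upward.

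These sizes rest on 22-25 evaluable Stage 1-2 patients, a simple threshold for switching, and exactly 37 evaluable in total. The sponsor can replace the range with one figure from its own records. The documents do not support reading this as an arithmetic error, as an unconditional breach of 5% by the ORR test, as a demonstrated loss of power, or as a fault in the pooled PFS6 test.

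**What to change.** In Sections 8.4.1 and 8.6.1:

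1. Report ORR with an exact 95% CI separately for Stages 1-2 and for the Expansion Cohort, with the Expansion result as the independent estimate beside the pooled one.
2. Label the pooled ORR test nominal. State that 77% and 88% are fixed-sample figures that do not account for the data-driven endpoint change, and give conditional type I error and power for the Stage 1-2 responder and evaluable counts on file.
3. Report Stage 1-2 PFS6 against its original 25%/50% decision rule as the original primary result.

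A formal test in the Expansion Cohort alone is not required. At 3 or more of 15 it has error 3.6% but only 60% power, falling to 44-55% with 12-14 evaluable, and that cohort follows the Safety Cohort schedule rather than that of the 18 Stage 2 patients.

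The cost is SAP wording and one extra table; no new patients or data are needed. The Expansion estimate will be imprecise (3/15 has an exact 95% CI of about 4% to 48%), and the pooled result will carry less confirmatory weight.

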4.3.6.2 Secondary Efficacy Endpoints

Proportion with PFS at 6 months (%PFS6) %PFS6 will be a key secondary endpoint for the overall study. In advanced biliary cancers treated with standard \geq 2nd line systemic chemotherapies, retrospective studies report median PFS of only approximately 2 to 3 months (corresponding to %PFS6 of approximately 20% (H_0) assuming normal distribution).^{2,4,10} A target %PFS6 of 40% (H_1) on treatment with pembrolizumab plus induction GM-CSF would represent a clinically meaningful improvement. Locally-assessed RECIST 1.1¹ will be used to determine progression.

Overall survival will be measured as another key secondary endpoint with the hypothesis that the median overall survival will be increased compared to a historical control median OS of 6.7 months from start of standard second line chemotherapy for advanced biliary cancers.⁶

An additional secondary efficacy endpoint is DOR, defined as time from first RECIST 1.1 response to disease progression in subjects who achieve a PR or better, as a clinically-relevant measure of efficacy. The duration of response or disease stabilization with 2nd line conventional chemotherapy in biliary tract cancers is very short, with median PFS only approximately 2-3

months on standard 2nd line therapies, and the majority of objective responses transient, lasting less than 6 months.^{2,37}

Re-induction and Second Course efficacy endpoints will also be described.

4.3.6.3 Safety Endpoints

Safety is a key secondary endpoint for this novel combination. The combination of GM-CSF plus ipilimumab showed an improved toxicity profile compared to ipilimumab alone with significantly lower rates of treatment-related grade 3-5 adverse events (44.9% versus 58.3%, p=0.04),³⁴ but the safety of pembrolizumab in combination with induction GM-CSF has not been studied in humans. The interim safety analysis after 9 patients in the Safety Cohort completed 3 cycles of therapy (1 cycle of pembrolizumab followed by 2 cycles with GM-CSF induction plus pembrolizumab, for total of 9 weeks in the Safety Cohort) or been removed for related toxicity events showed acceptable safety to continue enrollment to the Efficacy Cohort (see Section 4.3.5). The interim safety analysis showed that related ≥ Grade 3 toxicity rate during the first 3 cycles did not exceed 50%, a target set based upon the safety profile of standard chemotherapy in biliary tract cancers, and based upon the reported rate of related Grade 3-5 toxicity of approximately 45% for the combination of ipilimumab plus GM-CSF in advanced melanoma.^{9,34} The all-cause Grade 3 or 4 toxicity rate was approximately 70% in advanced biliary cancer patients treated with combination of standard 1st line chemotherapy with gemcitabine plus cisplatin in the ABC-02 trial,⁹ while the rate of Grade 3 or 4 toxicity was reported as 32% for 2nd line chemotherapy (predominantly 5-fluorouracil-based combinations) in a multicenter, retrospective AGEO analysis.⁶

Re-induction and Second Course safety will also be described at completion of study.

4.3.6.4 Biomarker Research

4.3.6.4.1 Tumor and TIIC PD-L1 Expression by Immunohistochemistry (IHC)

Tumor and/or TIIC PD-L1 expression by IHC are associated with an increased likelihood of response to immune checkpoint inhibition with PD-1 inhibitors in some cancer types.³⁸ A pooled analysis of 20 trials including 1475 patients with melanoma, non-small cell lung cancer (NSCLC), and genitourinary cancer showed a significant interaction between PD-L1 expression and response overall, with overall RR 34.1% vs. 19.9% (p<0.0001).³⁸ Response rates were significantly higher in PD-L1+ melanoma and NSCLC but no significant difference in response rate was observed according to PD-L1 status for genitourinary cancers, and a significant proportion of patients with PD-L1-negative tumors achieved tumor response to PD-1 inhibition across tumor types.

It is not known whether tumor PD-L1 expression is a predictive biomarker for response in biliary cancers, as the KEYNOTE-028 biliary cohort required PD-L1 expression for eligibility⁵ and the unselected KEYNOTE-158 biliary cohort results have not been reported. Intra-tumoral spatial and temporal heterogeneity in PD-L1 expression may also confound interpretation of tumor PD-L1 expression in archival pre-treatment samples which, in some cases, may have been harvested long before start of treatment.

Priming by an induction course of GM-CSF could also induce expression of PD-L1 in tumors or in TIIC such as tumor-associated lymphoid cells or monocytes, as has been demonstrated with administration of GVAX in pancreatic tumors.³¹

Based upon these findings which suggest that pre-treatment tumor PD-L1 expression may not be essential for response to treatment with the combination of pembrolizumab plus induction GM-CSF, tumor PD-L1 expression by IHC is not required as an integral biomarker for eligibility but will be tested as an integrated biomarker and secondary objective. Archival tumor biopsy or resection samples will be accessioned and tested centrally in batch at end of study for PD-L1 expression using an approved IHC assay (QualTek Laboratories). It is expected that the majority of samples will have been obtained pre-treatment. Treatment history at time of tumor sampling for each case will be documented in case report forms (CRFs), and an exploratory analysis may be conducted to compare proportion with PD-L1 expression based upon whether sample was obtained pre-treatment or after treatment with prior chemotherapy. An exploratory analysis will also be performed to compare tumor PD-L1 status in primary versus metastatic sites and according to anatomic location of the primary biliary cancer (e.g., intrahepatic CCA, extrahepatic CCA, GBC) or the metastatic site (e.g., liver vs. non-liver).

Paired primary and metastatic site tumor samples from the same patient will be tested and described when available. On-treatment or post-treatment tumor samples will also be analyzed if available in cases for which tumor resection or biopsy is required for clinical care (e.g. palliative metastatectomy, biopsy of an equivocal lesion to confirm progression, or if fiducial placement is required for palliative radiotherapy). PD-L1 expression will also be measured in on-treatment tumor biopsy samples obtained on pembrolizumab therapy and on combination therapy in patients enrolled to the Expansion Cohort.

4.3.6.4.2 Peripheral Blood Mononuclear Cell (PBMC) Immune Cell Subsets, TCR Clonotype Frequency and Diversity, and Other Analyses

Research blood samples will be collected from all patients at baseline, at multiple time points during treatment, and at progression (see Section 6.0 – Study Flow Chart). Whole blood will be processed into PBMC and cryopreserved at the UCSF Immune Monitoring Core for future analyses in batch at completion of study, pending funding and if warranted based upon clinical outcomes.

PBMC samples may be used to characterize immune cell subsets and T cell receptor (TCR) sequencing. Other analyses including immune cell gene expression profiling may be performed depending on adequacy of samples available, funding, and evolving biomarker data from other immune checkpoint inhibitor studies. [name] laboratory has demonstrated that treatment with the combination of CTLA-4 blockade plus GM-CSF results in expansion of activated effector CD8+ T cells as well as expansion of tumor antigen-specific T cells in patients with advanced prostate cancer.^{33,39} [name] laboratory and collaborators also have shown that checkpoint blockade by treatment with CTLA-4 inhibition in patients with metastatic prostate cancer and melanoma can increase T cell clonotype repertoire and diversity.^{33,40} Circulating immune cell subsets will be measured using flow cytometry and Cytof as has been previously described.^{33,39} The frequency of individual clonotypes, and the diversity of overall clonotype repertoire, will be measured by next-generation sequencing.⁴⁰ Baseline and changes on treatment in PBMC immune

cell subsets, TCR clonotype frequency and diversity, and gene expression profiles may be examined for relationship to clinical outcomes including PFS, RR, DOR, OS, and CA 19-9 response.

In the initial Safety Cohort (n=9) and the Expansion Cohort (n=15), PBMC samples for TCR analyses are collected before and after pembrolizumab alone in Cycle 1, followed by after the combination of pembrolizumab plus GM-CSF in Cycles 2 and 3. In the Efficacy Cohort (n=18), PBMC samples are collected before and after start of combination pembrolizumab plus induction GM-CSF, then on pembrolizumab monotherapy after completion of 2 cycles of GM-CSF. The variation in schedules of GM-CSF administration will enable intra-patient and inter-patient comparisons of immune cell profiles, TCR clonotype frequency and diversity, and other analyses pre-treatment, after pembrolizumab alone, and after the combination of pembrolizumab plus GM-CSF, as well as inter-patient comparisons between pembrolizumab and the combination of pembrolizumab plus GM-CSF after the first cycle, to better understand the relative impact of pembrolizumab alone and in combination with GM-CSF in this non-randomized study.

